### **Intervention (CPAP)**

Participants will be evaluated by a sleep specialist who will confirm eligibility for CPAP treatment. Eligible participants will be referred to VitalAire for initiation of treatment, following a standard protocol for use in the home (see Appendix 2). CPAP treatment will continue until the next visit for the main study, between 4-7 months based on the timing of the evaluations, after which the OSA study will end.

### **Post Intervention**

At the end of the study, participants will be referred to the sleep clinic where the sleep nurse will facilitate obtaining a device as per usual clinical care (private insurance, self-funded, welfare, second hand, etc). Participants who opt to buy the CPAP machine that they have been using will have a 20% discount. There may be a gap between the end of the study and allocation of a new device; this fact is mentioned in the informed consent document. All participants will be able to keep their mask.

### **Measurement**

Four types of measures are under study: (i) cognitive ability; (ii) self-reported cognitive symptoms; (iii) adherence to the CPAP treatment; and (iv) cohort.

- (i) Cognitive ability will be measured using the B-CAM which comprises computerized cognitive tests and yields a score on a continuous metric [30].

## **Effect of Continuous Positive Airway Pressure (CPAP) treatment on cognitive ability in HIV+ individuals with obstructive sleep apnea (OSA): A pilot study**

The values to be used will be those collected during the scheduled platform evaluations which occur 9-12 months apart.

- (ii) Self-reported cognitive symptoms will be measured using the C3Q (Communicating Cognitive Concerns in HIV) collected during the scheduled platform evaluations which occur 9-12 months apart.
- (iii) Adherence to the CPAP home treatment will be obtained from the CPAP device directly through its telemonitoring function, which is done by activating modems on CPAP machines and having the data transferred onto the Compliance Management Solutions. The granularity of the data will yield a continuous metric of sleep-minutes of use. Reasons for poor adherence and tolerance will be obtained by telephone contact or at clinical visits with the sleep specialist.
- (iv) Three cohorts will be compared: (i) the intervention cohort comprising all those approached who agreed to enter; (ii) the refuser cohort comprising all those approached who declined entry; and (iii) control cohort comprising eligible persons who were not approached, and hence were not given the opportunity to accept or decline.

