**PROTOCOL SUMMARY**

Full Title	Effect of Continuous Positive Airway Pressure (CPAP) treatment on cognitive ability in HIV+ individuals with obstructive sleep apnea (OSA): A pilot study
Short title	HIV and CPAP
Sponsor	McGill University
Funding	Canadian Institute of Health Research (CIHR) CPAP and masks for the duration of the study are provided in-kind by Resmed and cost of visits related to its initiation and calibration are provided in-kind by VitalAire
Principal Investigators	[name], [name], [name]
Associate investigators	[name], [name]
Objectives	
The primary objective is to estimate among people with HIV and obstructive sleep apnea, the extent to which 4-7 months of CPAP impacts on the primary outcome of cognitive ability (B-CAM), in comparison to individuals who screen positive for OSA but are not participating in the sleep apnea intervention.
 
An exploratory objective is to identify whether the changes are similar on measured cognitive ability and on self-reported cognitive symptoms.
 
The explanatory objective is to relate degree of adherence to CPAP to change in cognitive outcomes.

Study Population	
Inclusion Criteria
 

• Participants in the cohort study “Understanding and Optimizing Brain Health in HIV Now”

• Screened positive for OSA using the Berlin or the STOP-BANG (completed as part of the main study visits)

• Have been on a stable HAART regimen for > 6 months

• B-CAM ≤ 29

• Have not had a change in medications that could potentially interfere with sleep or cognition in the past 4 months.

• Willing to use CPAP as per instructions

• Able to comply with follow-up visit assessments

• Able to communicate in English or French

• Have at least one remaining visit in the main cohort study

 
Exclusion Criteria
 

• Already treated for OSA

**Effect of Continuous Positive Airway Pressure (CPAP) treatment on cognitive ability in HIV+ individuals with obstructive sleep apnea (OSA): A pilot study**

	

• Ongoing involvement in night shift work

• Presence of restless legs syndrome requiring immediate specific treatment

Study Design	Quasi-experimental single-arm, pre-post design will be carried out over a period of 4-7 months.

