CPAP has established efficacy in improving cognition. A meta-review involving review articles meeting pre-determined strict criteria, concluded that CPAP use improved executive function, long-term verbal and visual memory, attention/vigilance and global cognitive functioning [22]. Another meta-analysis also found that individuals with OSA demonstrated medium to very large impairments executive dysfunction, independent of age and disease severity, which showed small to moderate improvements following CPAP treatment [23]. In the context of Alzheimer's disease, Ancoli-Israel et al. conducted a randomized double-blind placebo-controlled trial to determine whether CPAP use resulted in improvements in neuropsychological test scores. Although the study was underpowered to make definitive conclusions about improvements within specific cognitive constructs, exploratory post hoc examination of score changes suggested that CPAP use by individuals with OSA yielded some benefits; these included improvements in episodic verbal learning and memory and some aspects of executive functioning such as cognitive flexibility and mental processing speed [24].

Although CPAP has been associated with improvements in cognitive functioning in the general population, its effectiveness in improving cognition in HIV+ individuals has never been previously tested. Given that the cognitive disturbances in this population are multi-factorial, determining whether treatment of OSA in this population improves cognition is key in improving the clinical management of HIV+ individuals, both for its negative impact on cognition but also more generally for their health.

Obstructive sleep apnea in the cohort “Understanding and Optimizing Brain Health Now”. Cohort participants (N=840) are studied prospectively over a 27-month period with visits every 9 months. Patients complete a computer-based evaluation of cognitive ability, the B-CAM, as well as questionnaires on socio-demographic characteristics, symptom status, functional status, health perception and quality of life. Given the high prevalence of OSA reported in the population, participants complete questions that, combined with other values already documented, support the scoring of two screening questionnaires for OSA, the Berlin [25, 26] and the STOP-BANG [27, 28] (see

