### **STUDY HYPOTHESIS**

Given there is no expectation for improvement in cognitive ability in this population in the absence of treatment for sleep apnea, we hypothesize that, over 4-7 months weeks of CPAP use, an improvement in cognition will occur, and if this is observed in 7 or more of 30 people, this response frequency is unlikely to have occurred by chance.

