### **Screening:**

Brain Health Now study participants who screen positive for the presence of OSA, meet inclusion/exclusion criteria based on the information already available as part of the main study questionnaires and who, on initial enrolment, have agreed to be contacted for sub-studies, will be approached for participation. Those who agree to participate and provide informed consent will be referred for a polysomnography (sleep study). Those with confirmed OSA will continue to the intervention phase.

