## **Effect of Continuous Positive Airway Pressure (CPAP) treatment on cognitive ability in HIV+ individuals with obstructive sleep apnea (OSA): A pilot study**

CAM score and C3Q. The analysis will focus on estimating the proportion of responders. A sample size of 30 participants will provide sufficient power for within-group analysis. With the assumption that the outcome is drawn from a binomial distribution with an expected probability of response of 10% (N=3) with no intervention, 30 subjects in the intervention group will allow detection of a positive response, with 80% power and  $p<0.05$ , if 7 or more persons respond (stattrek.com binomial calculator.) The proportion of responders on the different cognitive outcomes will also be estimated.

A secondary analysis will relate adherence to CPAP to change in cognitive outcomes using linear regression adjusting for age, sex, weight, baseline sleep satisfaction.

For between-cohort comparisons of cognitive outcomes, generalized estimating equations (GEE) will be used to permit both the baseline and post-intervention measures to be included along with the within-person correlation. A linear GEE will be used as the outcomes are continuous although a binary response was used for the primary objective. The model will include the indicator variable for cohort (CPAP, refuser, or control), time (assessment 1, 2), as well as confounding variables of age, sex, education, BMI, and comorbidity. As the control cohort will be very much larger than the intervention cohort, statistical comparisons have sufficient power to detect effect sizes of 0.5 or greater, suitable for a pilot study. The parameter estimated from GEE is equivalent to an adjusted effect size (adjusted between cohort effect divided by correlation adjusted standard error).

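### The pre-post B-CAM change spans 9-12 months, not the stated 4-7 months of CPAP, and the 10% null behind the 7-of-30 responder rule has no time window

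*Protocol*

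**What the plan says.** The Protocol Summary gives the design as "Quasi-experimental single-arm, pre-post design will be carried out over a period of 4-7 months". The Study Hypothesis places the benefit within the CPAP period and attaches the decision rule to it: "an improvement in cognition will occur, and if this is observed in 7 or more of 30 people", the result is taken as unlikely to be chance. The primary objective likewise names the impact of 4-7 months of CPAP.

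The Measurement section fixes which B-CAM scores are used: "The values to be used will be those collected during the scheduled platform evaluations which occur 9-12 months apart". It says the same for the self-reported C3Q. The Background gives a different spacing: "Cohort participants (N=840) are studied prospectively over a 27-month period with visits every 9 months".

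The treatment window is set by the cohort calendar. Under Intervention (CPAP): "CPAP treatment will continue until the next visit for the main study, between 4-7 months based on the timing of the evaluations". Before that, the Screening section finds people who "meet inclusion/exclusion criteria based on the information already available as part of the main study questionnaires", and then: "Those who agree to participate and provide informed consent will be referred for a polysomnography (sleep study". A sleep specialist confirms eligibility before CPAP begins. No B-CAM at the start of CPAP is described.

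Statistical Analysis and Sample defines a responder by a half-SD improvement and tests the count in 30 people against a 10% response rate without intervention. It gives no period for that 10%. It also describes a linear GEE across cohorts: "The model will include the indicator variable for cohort (CPAP, refuser, or control), time (assessment 1, 2", with confounders.

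**The concern.** The plan names one interval and measures another. The pre score is taken at a routine visit before recruitment steps and CPAP start; the post score is taken at the next routine visit. Whatever happens to B-CAM between the first visit and the first night of CPAP is part of the change that classifies a person as a responder.

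In the responder analysis nothing removes that part. It has no comparison group; its only protection is the assumed 10% rate. If that rate was meant for 4-7 months, or for no particular period, it may not describe how often untreated people gain half an SD across 9-12 months. The rule sits close to its limit, so a modest error in the 10% would undo the claim that 7 responders are unlikely by chance. The protocol says that the binary response was used for the primary objective, so this rule is not peripheral.

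A second, smaller consequence is that the quantity estimated is not the one named in the objective. The treated share of the interval varies from person to person, which dilutes any CPAP effect on the measured change and adds noise to the regression of cognitive change on adherence.

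**Working it through.** **1. Untreated time inside the measured interval.**

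Inputs: visit interval 9-12 months (Measurement) or 9 months (Background); CPAP 4-7 months, ending at the second visit (Intervention). Untreated months = visit interval minus CPAP duration.

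| Visit interval | CPAP | Untreated | Untreated share | Treated share |
|---|---|---|---|---|
| 9 | 7 | 9 - 7 = 2 | 2/9 = 22% | 78% |
| 9 | 4 | 9 - 4 = 5 | 5/9 = 56% | 44% |
| 12 | 7 | 12 - 7 = 5 | 5/12 = 42% | 58% |
| 12 | 4 | 12 - 4 = 8 | 8/12 = 67% | 33% |

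The range is 2-8 months, or 2-5 months under the 9-month schedule. Eight months pairs the longest interval with the shortest treatment and is an extreme. In no combination is the untreated part zero.

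**2. The plan's own cut-off.**

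Inputs: n = 30, null rate 10%, p<0.05, cut-off 7 (Statistical Analysis and Sample). Exact binomial upper tail:

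- P(X ≥ 6 | 30, 0.10) = 0.0732
- P(X ≥ 7 | 30, 0.10) = 0.0258

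So 7 is the smallest count with one-sided p<0.05, and the plan's figure reproduces. The stated 80% power is a separate matter and is not used here.

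**3. How much the rule depends on the 10%.**

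Type I error of the rule is P(X ≥ 7 | 30, p), where p is the true half-SD response rate without CPAP over the full visit interval. The documents give no such rate, so the values other than 10% are assumptions.

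| Untreated rate p | P(X ≥ 7) | Smallest cut-off with one-sided p<0.05 |
|---|---|---|
| 10% (plan) | 0.026 | 7 |
| 12% | 0.061 | 8 |
| 15% | 0.153 | 9 |
| 20% | 0.393 | 11 |

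Solving P(X ≥ 7 | 30, p) = 0.05 gives p of about 11.5%. The margin between the planning value and the point where the rule fails is about 1.5 percentage points.

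**4. The between-cohort comparison.**

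Refusers and controls belong to the same cohort and are assessed at the same scheduled visits. Their change covers the same kind of interval, so calendar time and repeat testing are largely shared. What remains there is that the contrast describes change over 9-12 months with CPAP in 33% to 78% of it, not the effect over a 4-7 month window.

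**The case against.** The interval is disclosed. The Measurement section states it for both outcomes, the Intervention section ties the end of CPAP to the next cohort visit, and the summary allows up to 12 months of involvement. Routine visits are the natural data source for a trial nested in a cohort, and this is a pilot. All of that stands as an explanation, but it does not reconcile the 4-7 month design statement and hypothesis with the scores actually used.

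The primary objective is worded as a comparison with people not in the intervention, and the GEE makes that comparison at matched visits. This stands, and it confines the main problem to the responder rule.

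A reader might go further and infer that the lead-in inflates the apparent CPAP effect. The documents do not support that. Untreated months could bring a practice gain, no change, or decline, and decline would count against CPAP. The hypothesis itself assumes no improvement without treatment. If the 10% was intended for the full visit interval and is right, the cut-off stands and only the description is wrong.

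A reader might also infer that regression to the mean after selection on B-CAM of 29 or less falls in the untreated months. It does not belong to any stretch of time. It appears at re-measurement, depends on the cut and the test-retest correlation, and would be the same had CPAP begun on the day of the baseline visit. It bears on whether 10% is a sound null, but does not measure the effect of the lead-in.

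**Conclusion.** The point holds as an inconsistency with a real consequence for one analysis. The stated 4-7 month pre-post change is in fact a change between visits 9-12 months apart, with 2-8 untreated months before CPAP (2-5 at 9-month spacing). The 7-of-30 rule treats the whole change as response to CPAP and relies on a 10% rate with no period attached. Its one-sided type I error is 0.026 if 10% is right for the visit interval, and above 0.05 beyond about 11.5%.

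This rests on the protocol's own intervals and an exact binomial calculation. Rates above 10% are assumed for illustration; nothing in the document shows that the true rate is higher, and the sign of any pre-CPAP change is unknown. For the GEE the issue is mainly labelling and dilution. The correction should be made, because it decides what a count of 7 can be said to show.

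**What to change.** 1. Restate the design, hypothesis and estimate as change over the 9-12 month visit interval that contains 4-7 months of CPAP.
2. State that the 10% no-intervention rate refers to that same interval. Take it from, or check it against, the half-SD responder rate of eligible controls over the same visits. If it differs, re-derive the 7-of-30 cut-off.
3. Base the conclusion about effect on the cohort-by-time contrast, matched on visit interval, using actual visit dates and the B-CAM visits the cohort already collects. Controls are already defined as eligible people who were not approached, so the same B-CAM criterion only needs to be made explicit for their baseline visit.
4. Do not replace the cohort contrast with a linear term for months on CPAP. It would be estimated from about 30 people over a narrow range and would put a model assumption in place of the comparison the objective names. It could serve as a sensitivity analysis.
5. Reconcile the visit spacing given in the Background (9 months) and in Measurement (9-12 months).

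The cost is protocol wording and a little more analysis work. No extra B-CAM session is needed. The downside is that the control data may call for a higher, less favourable cut-off.

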### **Procedures**

Patients diagnosed with OSA will be referred to VitalAire, a company that has agreed to loan Resmed CPAP devices, free-of-charge, to participants in this study (Appendix 3: Confirmation of collaboration). Staffs at VitalAire are under legal obligation to protect the confidentiality of information. Procedures for use of the devices will be explained to the patients. Follow-up with VitalAire staff will be done according to standard clinical protocols (see attached, Appendix 2). Patients may have as many visits with the respiratory therapist of VitalAire as needed for adjustments to their devices, at no cost. Typically patients will be contact by telephone one week after initiation and have follow-up in person with VitalAire after 1 month of CPAP use, but this may vary according to needs and availability.

During the course of CPAP use, the device automatically monitors various parameters which are used to monitor compliance in addition to residual apnea/hypopnea index (AHI) to ensure the settings are optimal. These data are obtained on line via the telemonitoring function and communicated by VitalAire to the study team. A separate consent will be signed at the same time as the consent for the OSA study, giving staff at VitalAire permission to communicate information to the study team (see Appendix 4).

As part of routine clinical care, patients will have a follow-up with a sleep specialist three months into the initiation of their CPAP to verify their clinical status and troubleshoot any issues with CPAP use. Additional visits will be scheduled if needed. A visit will also occur at the end of the study to plan post-study treatment.

### **Statistical Analysis and Sample**

Basic descriptive statistics will be used to characterize the participants including values on the all outcomes. Each person will be classified as a cognitive responder or not based on change on B-CAM. Responder status will be defined as improvement of  $\frac{1}{2}$  SD in B-

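### The within-group test reduces the continuous B-CAM change to a half-SD responder count judged against an unsourced 10% untreated rate, so its false-positive rate depends on a retest correlation the protocol does not give

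*Protocol*

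**What the plan says.** The Measurement section states that B-CAM "yields a score on a continuous metric". Under Statistical Analysis and Sample the score is then split: "Each person will be classified as a cognitive responder or not based on change on B-CAM". The cut is half an SD ("Responder status will be defined as improvement of" that amount), without saying whether this is the SD of baseline scores or of change.

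The sample size rests on the count. The plan takes an "expected probability of response of 10% (N=3) with no intervention", claims 80% power at p<0.05 if 7 or more respond, and concludes that "A sample size of 30 participants will provide sufficient power for within-group analysis". The Study Hypothesis section starts from the premise that "there is no expectation for improvement in cognitive ability in this population in the absence of treatment for sleep apnea", and adds that "if this is observed in 7 or more of 30 people, this response frequency is unlikely to have occurred by chance".

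The between-cohort comparison stays on the continuous scale, and the plan acknowledges the difference: "A linear GEE will be used as the outcomes are continuous although a binary response was used for the primary objective". No source is given for the 10%. No SD of change, mean change or true response rate under the alternative is stated.

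**The concern.** The premise in the hypothesis, that people do not improve untreated, is most naturally a statement about mean change, and the scores can test it directly. A count above a cut can test it only through a second assumption: what share of untreated people cross half an SD through measurement noise alone. The plan sets that share at 10% without support. If scores are noisier than this implies, people cross the cut in both directions, responders appear without any shift in the mean, and 7 of 30 is reached by chance far more often than the plan believes. The split also discards how far each person moved, which can cost power in a study fixed at 30. At stake is whether a positive pilot result, meant to justify a larger study, means what the protocol says it means.

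**Working it through.** **Inputs from the Protocol:** n = 30; untreated rate p0 = 0.10; success at 7 or more; cut of half an SD; stated power 80%, p<0.05. The only figure available for a true rate is 7/30 = 0.233, which is also the rejection count. The responder definition also mentions C3Q; the calculations below use B-CAM alone.

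**1. The plan's own figures (exact binomial, n = 30).**
- P(X ≥ 7 | 0.10) = 0.026, consistent with p<0.05. A cut-off of 6 gives 0.073, so 7 is the smallest valid count.
- P(X ≥ 7 | 7/30) = 0.570. The stated 80% is not reproduced.
- Solving P(X ≥ 7 | p) = 0.80 gives p = 0.287.

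**2. The same effect on the continuous scale.** Assume normal change, mean zero untreated, and the same shift for everyone.
- Shift in SDs of change = z(0.90) − z(1 − 7/30) = 1.282 − 0.728 = 0.554.
- One-sample t-test, n = 30, noncentrality 0.554 × √30 = 3.03: power 83.4% (two-sided 5%), or 83.8% one-sided at the rule's actual alpha of 0.026.
- 80% power, two-sided 5%, needs a mean change of 0.53 SD of change.

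**3. Only a fraction f improves, overall rate still 7/30.** Improvers respond at rate q = (7/30 − (1 − f) × 0.10)/f; simulated two-sided t-test power:

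| f | q | t-test | 7-of-30 rule |
|---|---|---|---|
| 0.2 | 0.77 | 37% | 57% |
| 0.3 | 0.54 | 46% | 57% |
| 0.5 | 0.37 | 62% | 57% |
| 1.0 | 0.23 | 83% | 57% |

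**4. Calibration with no CPAP effect and no selection.** Read half an SD as half a baseline SD, with equal SDs at both visits and retest correlation r (assumed range). SD of change = √(2(1 − r)) baseline SDs; null responder rate = P(Z > 0.5/SD of change); the chance of meeting the rule is the binomial tail at that rate.

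| r | SD of change | null responder rate | 7-of-30 rule met |
|---|---|---|---|
| 0.92 | 0.40 | 10.6% | 3% |
| 0.9 | 0.45 | 13.2% | 9% |
| 0.8 | 0.63 | 21.5% | 47% |
| 0.7 | 0.77 | 25.9% | 69% |

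A two-sided 5% t-test is significant upward in 2.5% of trials in every row. Conversely, a 10% rate requires SD of change = 0.5/1.2816 = 0.390, so r = 1 − 0.390²/2 = 0.924. If half an SD means the SD of change, the null rate is P(Z > 0.5) = 30.9% and the rule is met in 86% of trials.

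**5. Adding entry selection, still no CPAP effect.** The position of B-CAM ≤ 29 in the cohort is not given. With the cut assumed at +0.5 cohort SD, simulated rule versus upward t-test:
- r = 0.924: 5% versus 8%
- r = 0.92: 7% versus 8%
- r = 0.9: 17% versus 9%
- r = 0.8: 69% versus 14%
- r = 0.7: 89% versus 19%

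With the cut at −0.5 SD and r = 0.924, the figures are 12% versus 22%.

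**The case against.** The strongest reply is that the continuous data are not lost. The primary objective is a comparison with people who screen positive but are not in the intervention, and the linear GEE addresses it on the continuous score; adherence is also related to change by linear regression. That stands, and it confines this point to the within-group test and its sample-size statement.

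A second reply is that a t-test against zero makes an untested assumption of its own, namely no untreated change on average. This also stands. With a practice gain of 0.2 baseline SD, no CPAP effect and SD of change 0.39, the t-test is significant upward in about 77% of trials (noncentrality 0.2/0.39 × √30 = 2.81), against 51% for the count. Neither analysis is controlled.

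Third, a responder endpoint is a legitimate choice in a pilot: the plan says that it focuses on the proportion of responders and judges feasibility partly by it. That supports keeping the proportion, but not testing it against an unsupported rate.

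Three stronger readings are tempting, and the documents support none of them:
- **That splitting makes 30 people worth about 16.** The efficiency φ(c)²/[p(1 − p)] is 0.524 with the cut at the 7/30 tail, and 30 × 0.524 = 15.7. This assumes the same normal shift for everyone. The Protocol gives no such model and describes cognitive disturbance in this population as multifactorial; step 3 shows the advantage can reverse.
- **That the split explains the fall from 80% to 57%.** It does not. The rejection count appears to have been used as though it were the true rate, and that could be corrected with the responder endpoint kept.
- **That the count is always the worse test under selection, as 69% versus 14% suggests.** That comparison takes r = 0.8, whereas the plan's 10% implies about 0.92, where the count is no worse. Much of the 69% reflects a wrong null rate: at r = 0.8 that rate is already 21.5% without selection.

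**Conclusion.** The point holds for the within-group test. The 7-of-30 rule controls its error only if about 10% of untreated people cross the cut. With a half-baseline-SD cut and zero mean change, that needs a retest correlation of about 0.92. Below this its false-positive rate rises quickly: 9% at 0.9, 47% at 0.8 and 69% at 0.7, against 2.5% for an upward-significant t-test. These figures assume normal change, equal variances and no selection; the correlations are an assumed range, since the Protocol gives none.

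The 57% power at a true rate of 7/30 and the 29% rate needed for 80% power are exact and follow from the Protocol's own inputs. The gain from a t-test (83% against 57%) is conditional on a common shift and may vanish or reverse if only some people improve. Selection at B-CAM ≤ 29 inflates both tests. The change is worth making because it removes the dependence on an unsourced responder rate; it does not make the single-arm result evidence of a CPAP effect.

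**What to change.** - **Test.** Make the within-group analysis the mean B-CAM change in the CPAP group with its 95% CI, by paired t-test. Keep the responder proportion, with an exact CI, as a descriptive secondary, and say which SD defines the half-SD cut.
- **Sample size.** Restate the sentence: 30 people give 80% power (two-sided 5%) for a mean change of about 0.53 SD of the change score; the 7-of-30 rule has 80% power only at a true response rate of about 29%.
- **Interpretation.** State that the mean change is uncontrolled, so practice effects and regression to the mean remain, and that the conclusion about CPAP rests on the between-cohort linear GEE.

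The cost is Protocol and SAP wording; no new data are needed. The downside is that the simple 7-of-30 headline becomes descriptive.

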### **STUDY DESIGN**

This study is part of a larger project based upon a cohort multiple randomized controlled design [29]. Within a fully characterized cohort (N=840) which is followed over time, people meeting the specific criteria for one or more interventions (here CPAP) are identified and a sample is randomly selected to receive the intervention; the remaining eligible persons who do not receive the intervention serve as controls. This design, when operationalized for one intervention, yields three cohorts: (i) the intervention cohort comprising all those approached who agreed to enter; (ii) the refuser cohort comprising all those approached who declined entry; and (iii) control cohort comprising eligible persons who were not approached, and hence were not given the opportunity to accept or decline. For the CPAP intervention, the duration of the study is 4-7 months.

Eligible patients will be identified among the Montreal participants (N=500) in the “Understanding and Optimizing Brain Health Now” cohort study who have screened positive for the possible presence of sleep apnea on either the Berlin or the STOP-BANG and experience some cognitive difficulties as measured by the B-CAM ( $\leq 29$ ). We will continue recruitment until 30 participants have used the CPAP device for a minimum of 4 months, on at least 30% of the nights with a median of  $\geq 4$  hours/night.

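### The 7-of-30 responder rule depends on an unsourced 10% untreated response rate and tolerates little more than 11%, while a half-SD B-CAM cut-off could give a higher rate from retest variation alone

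*Protocol*

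**What the plan says.** Under Statistical Analysis and Sample, each person is classed as a cognitive responder or not from the change in B-CAM. "Responder status will be defined as improvement of" ½ SD, and the sentence ends by naming both measures ("CAM score and C3Q"). Which SD is meant is not stated.

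The same section says "A sample size of 30 participants will provide sufficient power for within-group analysis". It assumes an "expected probability of response of 10% (N=3) with no intervention" and claims detection "with 80% power and" p<0.05 "if 7 or more persons respond". It later confirms that the binary response serves the primary objective. Study Hypothesis turns this into a claim about evidence: "if this is observed in 7 or more of 30 people, this response frequency is unlikely to have occurred by chance". The only reason offered there for a low untreated rate is that cognition is not expected to improve without treatment.

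On selection, Study Design limits entry to people who "experience some cognitive difficulties as measured by the B-CAM", with a score of 29 or less. Screening says eligibility is judged on data the main cohort already holds. Measurement says the outcome values come from the routine cohort visits, 9 to 12 months apart. No separate B-CAM before CPAP is described.

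**The concern.** A low mean expectation of change does not make individual half-SD rises rare. Two scores taken months apart differ through measurement error and ordinary fluctuation, so some untreated people will cross a half-SD line with no true improvement. How many depends on the retest correlation, which the protocol does not report.

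Selection adds to this. If the score that qualified a person is also the baseline, people admitted partly because of a chance low score will tend to drift upward at the next visit. That the two scores are the same is inferred from Screening and Measurement; the protocol does not say so outright.

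The count of responders is compared with a fixed 10% and not with observed controls, so neither effect is removed. If the true untreated rate is well above 10%, the pilot could report a cognitive response to CPAP when there is none. The section on anticipated results uses the proportion responding, together with adherence, to judge whether a further study is warranted.

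**Working it through.** **Inputs from the protocol.** n = 30; threshold 7; untreated rate 10%; p<0.05; cut-off ½ SD; entry at B-CAM ≤29.

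**Inputs assumed, because the protocol gives none.** Retest correlation r from 0.7 to 0.95; normal scores with equal SD at both visits; no true change and no practice effect; SD of the full cohort; 29 lying 0 to 1 SD above the cohort mean; response judged on B-CAM alone.

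**1. The plan's own figure.** With X ~ Binomial(30, 0.10), P(X ≥ 6) = 0.073 and P(X ≥ 7) = 0.026. Seven is the correct one-sided 5% threshold if 10% is true. The 80% power has no stated alternative: it needs a true response of about 28.7%, and at a true rate of 7/30 the power is 57%.

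**2. Slack in the rule.** Solving P(X ≥ 7 | 30, p) = 0.05 gives p = 0.115. An untreated rate only 1.5 percentage points above the assumed one uses up the 5%.

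**3. Untreated response without selection.** The change score, in cohort SD units, has SD √(2(1−r)). So P(change ≥ 0.5) = P(Z ≥ 0.5/√(2(1−r))).

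- At r = 0.8: 0.5/√0.4 = 0.791, giving 21.5%.
- At r = 0.9: 0.5/√0.2 = 1.118, giving 13.2%.
- Exactly 10% requires r = 1 − (0.5/1.2816)²/2 = 0.924.
- 11.5% is passed once r falls below about 0.913.

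**4. With selection.** Let X be the standardised baseline, Y the follow-up, and c the standardised position of 29. The rate is P(Y − X ≥ 0.5 | X ≤ c), with Y given X normal, mean rX and variance 1 − r². Integrating over X ≤ c for c = 1 and c = 0 gives the ranges below. Each rate is then put into P(X ≥ 7 | 30, p).

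| r | Rate, no selection | P(≥7), no selection | Rate, with selection | P(≥7), with selection |
|---|---|---|---|---|
| 0.70 | 25.9% | 69% | 29-36% | 81-95% |
| 0.80 | 21.5% | 47% | 24-29% | 59-81% |
| 0.90 | 13.2% | 9% | 14-17% | 13-24% |
| 0.95 | 5.7% | 0.1% | 6-7% | 0.2-0.4% |

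Most of the excess over 10% is plain retest variation. At r = 0.9 selection adds about 1 to 4 percentage points, and at r = 0.8 about 2 to 7. With only the lower half of scores admitted (c = 0), the rate falls to 10% near r = 0.94.

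**5. Which SD.** If the half SD were taken from the enrolled group, the cut-off would shrink. With the lower half selected, that SD is about 0.6 of the cohort SD. The untreated rate is then 31% at r = 0.9 (P(≥7) = 86%) and 20% at r = 0.95 (41%). This shows why the SD should be named; it is not used to size the problem.

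**6. Joint rule.** If B-CAM and C3Q must both improve, with r of 0.7 to 0.9 for each and a correlation between the two changes of 0 to 0.3, the unselected rate is about 2-10% and P(≥7) is at most 2.7%. With the lower half selected, r = 0.7 and change correlation 0.3, it is 14% and 13%.

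**The case against.** The strongest objection is that nothing in the protocol shows B-CAM to be unreliable enough for this to matter. That stands. A reader might infer that the cut-off lies inside retest noise and that untreated people will exceed 10%. The document does not support that as a fact: at r = 0.95 with the full-cohort SD the rule is conservative, and at r = 0.92 with 29 one SD above the mean it sits at about 5%.

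Second, the definition can be read as requiring improvement on both B-CAM and C3Q, which would largely remove the problem. B-CAM alone is the better-supported reading: the classification is introduced as resting on B-CAM change, responders on the different outcomes are estimated separately, and B-CAM is the primary outcome. The ambiguity is real all the same.

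Third, the protocol plans a linear GEE against cohort controls. The not-approached controls meet the same B-CAM limit, so that comparison largely offsets regression to the mean. A reader might infer that a larger trial would rest on measurement error alone; with this analysis planned and adherence also weighed, that goes too far. But the GEE does not protect the 7-of-30 rule, which has no comparator and carries the hypothesis and sample size.

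Finally, this is a pilot and a statistical analysis plan may exist. That lowers the priority, but the cut-off, the 10% and the decision rule are all fixed in the protocol.

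**Conclusion.** The point holds conditionally. The 10% untreated rate is unsourced, and the rule built on it tolerates no more than about 11.5%. Under the assumptions listed, the chance of a false positive runs from under 0.5% at r = 0.95, through 13-24% at r = 0.9 and 59-81% at r = 0.8, to 81-95% at r = 0.7. The protocol offers nothing to place B-CAM within that range over a 9-12 month interval. The claim in Study Hypothesis that seven responders would be unlikely by chance is therefore unsupported, not shown to be false. The result also depends on response being judged on B-CAM alone and, for the smaller selection part, on the qualifying score being the baseline. Should-fix for a pilot.

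**What to change.** 1. State that responder status for the primary analysis is a half-SD improvement on B-CAM alone, using the full-cohort SD, with C3Q response reported separately.
2. Before intervention results are examined, estimate the half-SD response rate over one cohort interval among eligible controls who were not approached (screen-positive, B-CAM ≤29). Use it in place of 10%, recompute the threshold, and restate power with a named alternative.
3. Alternatively, compare the responder proportion directly with those controls. This carries the uncertainty in their rate, which a fixed substitute does not.

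A cut-off at the 90th percentile of control change is another route, but it is itself an estimate and would not guarantee the intended error rate.

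The work is a wording change and one calculation on data the cohort already collects. The cost is a higher bar and lower stated power. As illustrations: at a control rate of 15% the threshold becomes 9 of 30 (P(X ≥ 9) = 0.028; P(X ≥ 8) = 0.070), and 80% power needs a true response of about 36%. At 25% it becomes 13 of 30 (P(X ≥ 13) = 0.022; P(X ≥ 12) = 0.051), and 80% power needs about 49%.

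The controls are also imperfect: they are only screen-positive, whereas treated participants have OSA confirmed by polysomnography and the 30 are counted by adherence. The report should say so.
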